#### 2.3.2.1 Durvalumab

Risks with durvalumab include, but are not limited to, diarrhea/colitis, pneumonitis/ILD, endocrinopathies (ie, events of hypophysitis/hypopituitarism, adrenal insufficiency, hyper- and hypo-thyroidism, type I diabetes mellitus, and diabetes insipidus), hepatitis/increases in transaminases, nephritis/increases in creatinine, rash/dermatitis, myocarditis, myositis/polymyositis, infusion-related reactions, hypersensitivity reactions, pancreatitis, serious infections, and other rare or less frequent inflammatory events including neuromuscular toxicities (eg, Guillain-Barre syndrome, myasthenia gravis).

For information on all identified and potential risks with durvalumab, please always refer to the current version of the durvalumab IB.

In monotherapy clinical studies, including a study in unresectable NSCLC in which patients received durvalumab following concurrent SoC platinum-based chemoradiotherapy (PACIFIC), AEs at an incidence of  $\geq 20\%$  include events such as fatigue, cough, decreased appetite, dyspnea, and nausea. Approximately 10% of patients discontinued the drug due to an AE. Please see the current version of the IB for a detailed summary of the monotherapy data including AEs, SAEs), and Common Terminology Criteria for Adverse Events (CTCAE) Grade 3 to 5 events reported across the durvalumab program.

The majority of treatment-related AEs were manageable, with dose delays, symptomatic treatment, and in the case of events suspected to have an immune basis, the use of established treatment guidelines for immune-mediated toxicity (see Section 8.4.5).

A detailed summary of durvalumab monotherapy AE data can be found in the current version of the durvalumab IB.

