### 5.1.2 Inclusion criteria assessed during the second screening period

#### **Criteria for second screening prior to randomization to treatment:**

- 14 CT scan of the chest and abdomen (including liver and adrenal glands) and brain MRI [preferred] or brain CT with IV contrast performed within the 28 days ± 7 days **prior to randomization** to confirm no evidence of RECIST 1.1-defined disease recurrence and/or metastasis.
- 15 Known tumor PD-L1 status determined at a central reference laboratory testing service using a validated Ventana SP263 PD-L1 immunohistochemistry (IHC) assay prior randomization. Patients with unknown PD-L1 status are not eligible for the study.
- 16 WHO/Eastern Cooperative Oncology Group (ECOG) performance status (PS) 0-1.
- 17 Complete post-operative wound healing must have occurred prior to randomization; patients must have recovered from all acute, reversible toxic effects from prior treatments (excluding alopecia) that could potentially adversely impact further administration of durvalumab/placebo according to the Investigator's judgment.
- 18 Must have recovered from all acute, reversible toxic effects from chemotherapy that could potentially adversely impact further administration of durvalumab or placebo according to the Investigator's judgment
- 19 Adequate organ and marrow function as defined below:

Hemoglobin  $\geq 9.0$  g/dL

Absolute neutrophil count  $\geq 1.5 \times 10^9/L$

Platelet count  $\geq 100 \times 10^9/L$

Serum bilirubin  $\leq 1.5 \times$  the upper limit of normal (ULN). This will not apply to patients with confirmed Gilbert's syndrome, who will be allowed in consultation with their physician.

Alanine aminotransferase (ALT) and aspartate aminotransferase (AST)  $\leq 2.5 \times$  ULN

Measured creatinine clearance (CL)  $\geq 30$  mL/min or Calculated CL  $> 30$  mL/min as determined by Cockcroft-Gault (using actual body weight)

Males:

$$\text{Creatinine CL (mL/min)} = \frac{\text{Weight (kg)} \times (140 - \text{Age})}{72 \times \text{serum creatinine (mg/dL)}}$$

Females:

$$\text{Creatinine CL (mL/min)} = \frac{\text{Weight (kg)} \times (140 - \text{Age})}{72 \times \text{serum creatinine (mg/dL)}} \times 0.85$$

20 Must have a life expectancy of at least 12 weeks

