3.3.5 Laboratory Data

Laboratory data will be collected throughout the study, from second screening to the second follow-up visit (12 weeks \pm 1 week after completion or discontinuation of study treatment i.e. durvalumab/placebo). Blood and urine samples for determination of hematology, clinical chemistry, and urinalysis will be collected as described in Section 8.2.1 of the CSP. For the definition of baseline and the derivation of post-baseline visit values considering visit window and how to handle multiple records, derivation rules as described in Section 4.1.2 will be used.

Change from baseline in hematology and clinical chemistry variables will be calculated for each postdose visit on-treatment. Common Terminology Criteria for Adverse Event (CTCAE) grades will be defined at each visit according to the CTCAE grade criteria using local or project ranges as required, after conversion of lab result to corresponding standard international (SI) units. The following parameters have CTCAE grades defined for both high and low values: Potassium, Sodium, Magnesium, and Corrected calcium.

Corrected calcium will be derived during creation of the reporting database using the following formula:

$$\text{Corrected calcium (mmol/L)} = \text{Total Calcium (mmol/L)} + ([40 - \text{Albumin (g/L)}] \times 0.02)$$

Creatinine clearance (CL) will be derived according to the Cockcroft-Gault formula (Cockcroft and Gault 1976).

Males:

$$\text{Creatinine CL (mL/min)} = \frac{\text{Weight (kg)} \times (140 - \text{Age at randomization})}{72 \times \text{serum creatinine (mg/dL)}}$$

Females:

$$\text{Creatinine CL (mL/min)} = \frac{\text{Weight (kg)} \times (140 - \text{Age at randomization})}{72 \times \text{serum creatinine (mg/dL)}} \times 0.85$$

Absolute values will be compared to the project reference range and classified as low (below range), normal (within range or on limits of range) and high (above range).

The maximum or minimum on-treatment value (depending on the direction of an adverse effect) will be defined for each laboratory parameter as the maximum (or minimum) post-baseline value at any time.

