4.2.9.3 Laboratory Assessments

Data obtained up until the 90 days following discontinuation of study treatment (i.e. durvalumab/placebo) or until the initiation of subsequent anti-cancer therapy (including radiotherapy, except for palliative radiotherapy) following discontinuation of study treatment (whichever occurs first) will be used for reporting. This will more accurately depict laboratory toxicities attributable to study treatment only as some toxicities up to 90 days following discontinuation of the study treatment are likely to be attributable to subsequent therapy. Any data post 90 days after the last dose of the study treatment will not be summarized.

Data summaries will be provided in SI units.

Shift tables for laboratory values by worst CTCAE grade will be produced, and for specific parameters separate shift tables indicating hyper- and hypo- directionality of change will be produced. The laboratory parameters for which CTCAE grade shift outputs will be produced are:

- Hematology: Hemoglobin (low and high); Leukocytes (low and high); Lymphocytes (low and high - count, absolute); Neutrophils (low - count, absolute); Platelets (low)

- Clinical chemistry: Alanine aminotransferase (ALT) (high), Aspartate aminotransferase (AST) (high), Alkaline phosphatase (ALP) (high), Total Bilirubin (high), Albumin (low), Magnesium (hypo and hyper), Sodium (hypo and hyper), Potassium (hypo and hyper), Corrected Calcium (hypo and hyper), Glucose (low), Creatinine (high), GGT (high), Amylase (high), Lipase (high)

In addition, all laboratory data will be listed.

Liver Enzyme Elevations and Hy's Law

The following summaries will include the number (%) of patients who have:

- Elevated ALT, AST, and Total bilirubin on-treatment
 - ALT $\geq 3\times - \leq 5\times$, $> 5\times - \leq 8\times$, $> 8\times - \leq 10\times$, $> 10\times - \leq 20\times$, and $> 20\times$ ULN on-treatment
 - AST $\geq 3\times - \leq 5\times$, $> 5\times - \leq 8\times$, $> 8\times - \leq 10\times$, $> 10\times - \leq 20\times$, and $> 20\times$ ULN on-treatment
 - Total bilirubin $\geq 2\times - \leq 3\times$, $> 3\times - \leq 5\times$, $> 5\times$ ULN on-treatment
 - ALT or AST $\geq 3\times - \leq 5\times$, $> 5\times - \leq 8\times$, $> 8\times - \leq 10\times$, $> 10\times - \leq 20\times$, $> 20\times$ ULN on-treatment

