 - ALT or AST $\geq 3\times$ ULN and Total bilirubin $\geq 2\times$ ULN on-treatment (Potential Hy's law): The onset date of ALT or AST elevation should be prior to or on the date of Total Bilirubin elevation

Individual patient data where ALT or AST (i.e. $\geq 3\times$ ULN) plus Total Bilirubin (i.e. $\geq 2\times$ ULN) are elevated at any time will be listed also.

Assessment of Thyroid Function Test Results

The following summaries will include the number and percentage of patients who have elevated or low thyroid stimulating hormone (TSH).

- TSH $> \text{ULN}$
- TSH $> \text{ULN}$ with TSH $\leq \text{ULN}$ at baseline
- TSH $> 3 \times \text{ULN}$
- TSH $> 3 \times \text{ULN}$ with TSH $\leq \text{ULN}$ at baseline
- TSH $> 10 \times \text{ULN}$
- TSH $> 10 \times \text{ULN}$ with TSH $\leq \text{ULN}$ at baseline

- TSH < LLN
- TSH < LLN with TSH \geq LLN at baseline

In addition, summaries will include shift tables comparing baseline value to maximum on-treatment value and baseline value to minimum on-treatment value. Thyroid function test data will be listed also.

Assessment of Renal Function Test Abnormalities

In addition to the analysis for serum creatinine, the number and percentage of patients with creatinine clearance (CrCl) rate on-treatment (derived per Section 3.3.5) meeting the following categories will be presented:

- Normal: CrCl \geq 90 mL/min
- Mild Impairment: CrCl \geq 60 - < 90 mL/min
- Moderate Impairment: CrCl \geq 30 - < 60 mL/min
- Severe Impairment: CrCl \geq 15 - < 30 mL/min
- Kidney Failure: CrCl < 15 mL/min

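### Creatinine clearance is tabulated without the baseline reference given to TSH, and high glucose is listed but not tabulated (SAP 4.2.9.3)

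*SAP*

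**What the plan says.** **Renal function.** The renal paragraph of SAP 4.2.9.3 states: "In addition to the analysis for serum creatinine, the number and percentage of patients with creatinine clearance (CrCl) rate on-treatment" will be presented in five categories: at least 90, 60 to below 90, 30 to below 60, 15 to below 30, and finally "Kidney Failure: CrCl < 15 mL/min". It refers to SAP 3.3.5 for the Cockcroft-Gault derivation. It mentions no baseline category and no shift. CrCl is not among the baseline characteristics in SAP 4.2.10.

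**Graded laboratory shifts.** The same section says "Shift tables for laboratory values by worst CTCAE grade will be produced". The chemistry list includes "Glucose (low), Creatinine (high), GGT (high), Amylase (high), Lipase (high", so creatinine is covered upward and glucose only downward. All laboratory values are also listed.

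**Thyroid, for comparison.** TSH counts are given overall and for patients who were not already abnormal at baseline, with shifts from baseline to both the maximum and the minimum on-treatment value.

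**Protocol.** Criterion 19 (section 5.1.2) requires a measured clearance of at least 30 mL/min, or a calculated one above 30, "as determined by Cockcroft-Gault (using actual body weight"). Section 2.3.2.1 names "type I diabetes mellitus, and diabetes insipidus" among the endocrine risks, and also names nephritis with raised creatinine. Section 8.3.12 lists type I diabetes and nephritis as events of special interest.

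**The concern.** Laboratory findings belong to the study's only secondary objective, and descriptive tables are the whole of the planned safety analysis. A safety table should separate what was present before dosing from what appeared afterwards, and it should look in the direction of the known risk.

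The CrCl table does not do the first in the mild and moderate rows, where patients may already sit at entry. The glucose output does not do the second: the direction that would accompany diabetes has no summary. A reader of the study report could take an imbalance in baseline renal function for a treatment finding, or see no glucose signal because only low values were tabulated.

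**Working it through.** The plan gives no figure for this point, so there is nothing to reproduce. The check compares sections and adds two illustrations on stated assumptions.

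**1. Which outputs refer to baseline (SAP 4.2.9.3)**

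| Parameter | Summary | Baseline reference |
|---|---|---|
| TSH | Counts and shifts, both directions | Yes |
| Creatinine | CTCAE shift, high | Yes |
| CrCl | On-treatment category counts | No |
| Glucose | CTCAE shift, low only | Yes, low side only |

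**2. Can impairment exist before dosing?** The SAP 3.3.5 formula is weight × (140 − age) / (72 × creatinine), times 0.85 for women. The patients below are invented; the documents give no baseline distribution.

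- Man, 65 years, 75 kg, 1.0 mg/dL: 75 × 75 / 72 = 78.1 mL/min, mild.
- Woman, 65 years, 65 kg, 0.8 mg/dL: 65 × 75 / 57.6 × 0.85 = 71.9 mL/min, mild.
- Woman, 75 years, 50 kg, 1.1 mg/dL: 50 × 65 / 79.2 × 0.85 = 34.9 mL/min, moderate.

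All three satisfy criterion 19 on renal function, and each would be counted in an impairment row with no change on treatment.

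**3. Why the creatinine shift only partly substitutes.** SAP 3.3.5 grades laboratory values against reference ranges. CrCl also depends on weight, age and sex, so the two can classify one patient differently. The third patient reaches 30 mL/min at a creatinine of 50 × 65 × 0.85 / (72 × 30) = 1.28 mg/dL, a rise of 0.18. Whether that changes her creatinine grade depends on limits the documents do not give.

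**4. How readable is an uncorrected row?** SAP 1.2 expects about 30 randomized patients; at 1:1 that is about 15 per arm, and 1/15 = 6.7 percentage points. Assume a proportion p of each arm has moderate impairment at baseline and there is no drug effect. With independent counts X and Y, each Binomial(15, p), P(|X − Y| ≥ d) is the sum of P(X = i) × P(Y = j) over all pairs at least d apart:

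| p | d = 2 | d = 3 |
|---|---|---|
| 0.10 | 0.35 | 0.12 |
| 0.20 | 0.49 | 0.25 |
| 0.30 | 0.55 | 0.32 |

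**5. Following a glucose rise through the outputs.**

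- Graded shift: not shown, because only the low side is tabulated.
- Other laboratory summaries in 4.2.9.3: these concern liver, thyroid and renal function.
- AE, AESI and imAE tables: shown only if reported as an event. Glucose is a protocol-mandated test (protocol Table 11). Under 8.3.7, deterioration in such a value is reported as an event only if it meets a seriousness criterion or causes discontinuation. If symptoms accompany it, the symptom is the event.
- Listing: shown.

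Protocol 8.3.7 justifies that reporting limit by saying the mandated laboratory results will be summarized in the study report. For high glucose, the SAP provides no such summary.

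**The case against.** A reader might infer that the planned outputs cannot show the renal or diabetes risk at all. The documents do not support that. The renal risk is named in the protocol together with raised creatinine, and the Creatinine (high) shift is baseline-referenced and addresses it directly; the CrCl table is expressly an addition. Diabetes and nephritis reported as events are counted in the AE, AESI/AEPI and imAE tables, including use of endocrine therapy. Concomitant medication is summarized by ATC code, so glucose-lowering treatment would be visible.

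The CrCl table also carries some information alone. Entry requires about 30 mL/min, so counts in the two lowest rows are essentially new since screening. The exception is a patient admitted on a measured clearance whose calculated value is lower.

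A reader might also infer that one patient could fall in several CrCl rows. That is weak. SAP 3.3.5, cited for the CrCl derivation, defines the minimum or maximum on-treatment value according to the adverse direction, and 4.1.2 repeats the extreme-value rule. The natural reading is one row per patient at the minimum, though 4.2.9.3 does not say so.

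The low-only glucose entry may follow from SAP 3.3.5, which omits glucose from the parameters graded in both directions. That list does not bind the shift outputs, however: hemoglobin, leukocytes and lymphocytes are shifted both ways without being on it. A range-based table needs no grade.

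Finally, the study is small and descriptive, every value is listed, and the SAP amendment history shows that laboratory summaries were deliberately reduced. This limits the importance of the point but does not remove the two gaps.

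**Conclusion.** The point holds in limited form. The mild and moderate CrCl rows mix pre-existing with new impairment, and the creatinine shift only partly makes up for it. High glucose is listed but not tabulated, and an isolated, non-serious rise can miss the AE tables as well.

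The effect is small: about 30 patients, exploratory tables, no inference at stake. The chance-imbalance figures assume 15 per arm and a baseline prevalence of 10% to 30%, which the documents do not give; they show that the moderate row is hard to interpret, not that an imbalance will occur. The documents do not support saying that the nephritis or diabetes risk goes unreported, or that the CrCl table is uninformative.

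**What to change.** In SAP 4.2.9.3:

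1. Present CrCl as a shift from baseline category to minimum on-treatment category, stating the minimum explicitly. This follows the method already used for TSH.
2. Add a glucose shift from baseline to maximum on-treatment value, using the SAP 3.3.5 scheme in which values are "classified as low (below range), normal (within range or on limits of range) and high (above range").

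The cost is two sentences and two small tables. Creatinine, glucose and weight are already collected at treatment visits, and endpoints, analysis sets and patient procedures do not change. High glucose values will need cautious reading: the protocol's laboratory table specifies no fasting status, and protocol Table 9 permits steroids in some circumstances. A footnote saying so would be enough.

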4.2.9.4 Electrocardiograms

Since ECGs are only collected as clinically indicated, abnormalities in ECG data obtained at any time during the study will be listed only.

4.2.9.5 Vital Signs

All vital signs data (SBP, DBP, pulse rate, temperature, respiratory rate and weight) will be listed only.

4.2.10 Demographics and Baseline Characteristics

The following will be summarized for all patients in the FAS and PD-L1 TC \geq 1% analysis set (unless otherwise specified) by treatment group:

- Patient disposition (all patients, including screening failures [split by whether or not ICF2a was signed] and reason for screening failure, and status in regards to the surveillance period)
- Important protocol deviations (FAS only)
- Inclusion in analysis sets (all patients)

- Demographics (age, age group [< 50 , $\geq 50 - < 65$, $\geq 65 - < 75$ and ≥ 75 years], sex, race and ethnicity)
- Patient characteristics at baseline (height, weight, weight group [< 70 , 70-90, > 90 kg], body mass index [BMI], BMI group [< 18.5 , $\geq 18.5 - < 25$, $\geq 25 - < 30$, ≥ 30 kg/m²])
- Patient recruitment by region, country and center
- Previous disease-related treatment modalities (chemotherapy, radiation therapy and immunotherapy) (FAS only)
- Disease characteristics at baseline (Easter Cooperative Oncology Group [ECOG] performance status, primary tumor location, histology type [squamous, non-squamous, other], tumor grade, and overall disease classification)
- Extent of disease at baseline
- TNM classification at baseline
- Disease related medical history (past and current) (FAS only)
- Relevant surgical history (FAS only)
- Nicotine use, categorized ([never, former, current])
- Stratification factors as per IWRS and eCRF

The data mentioned above will also be presented in listings. Additionally, a listing of EGFR/ALK results will also be provided.

4.2.11 Concomitant and Other Treatments

Information on any medications or therapies from first screening to 90 days after the last dose of study treatment (i.e. durvalumab/placebo) will be recorded in the eCRF. Thereafter, only subsequent regimens of anti-cancer therapy will be recorded in the eCRF.

Other anti-cancer therapies, investigational agents, and radiotherapy should not be given once the patient has completed curative intent therapy and while they are randomized and on study drug.

Medications received prior to, concomitantly, or post-study treatment will be coded using the World Health Organization drug dictionary (WHODD) Anatomical Therapeutic Chemical (ATC) classification codes. Concomitant medications/therapies will be summarized for the FAS by ATC classification codes.

For the purpose of inclusion in prior and/or concomitant medication or therapy summaries, incomplete medication or radiotherapy start and stop dates will be imputed as detailed in Section [4.1.2](#).

Prior, concomitant and post-study treatment medications and therapies are defined based on imputed start and stop dates as follows:

- Prior medications/therapies are those taken prior to study treatment with a stop date prior to the first dose of study treatment.
- Concomitant medications/therapies are those that started prior to study treatment and are ongoing at the first dose date of study treatment, or that started on or after the first dose date of study treatment but on or before the last dose date of study treatment.
- Post-study treatment medications/therapies are those with a start date after the last dose date of study treatment.

The following summaries will be produced for the FAS:

- Summary of allowed concomitant medications
- Summary of disallowed concomitant medications
- Summary of subsequent anti-cancer therapies (including radiotherapy)

All concomitant and other treatment data will be listed.

Missing coding terms should be listed and summarized as 'Not coded'.

4.2.12 Exposure

Exposure will be summarized for the safety analysis set.

The following summaries will be produced by treatment group:

- Total exposure
- Actual exposure
- Number of, and reasons for, interruptions and delays of study treatment
- Cumulative exposure over time for study treatment
- Number of treatment cycles received
- RDI

Exposure of durvalumab/placebo over time will be plotted in a line graph. The plot will show percentage of patients still on treatment against time since first dose.

For patients on study treatment at the time of the DFS analysis, the DCO date will be used to calculate exposure.

4.2.13 Coronavirus Disease 2019 (COVID-19)

Summaries of data relating to patients diagnosed with COVID-19 and the impact of COVID-19 on study conduct (eg, missed visits, delayed or discontinued study treatment [i.e. durvalumab/placebo], and other protocol deviations) may be generated. For AE and deaths, summaries of COVID-19 related events including infections and deaths maybe produced.

Supportive listings may be produced.

4.3 Surveillance Period

For the purpose of the CSR, data collected during the surveillance period may be included in listings for patients in the FAS only, and will be flagged to distinguish between data collected in the surveillance period and the treatment period.

Additional exploratory summaries and analyses may be performed on top of the summary of time to MRD+ emergence mentioned in Section 4.2.2.1.

5. INTERIM ANALYSES

5.1 Interim Efficacy Analysis

Prior to CSP V2.0, an interim analysis of OS was to be performed at the time of the DFS primary analysis.

Under CSP V2.0, no interim analyses will be performed.

